Study Design:	
After meeting eligibility criteria during screening, qualified subjects will undergo a 14-day run-in period during which they will use Vehicle BID bilaterally. If they meet eligibility criteria at baseline, they will be randomized 1:1:1 to receive ALY688 0.1% (n=40), ALY688 0.4% (n=40), or Vehicle (n=40). Dosing will be BID bilaterally. If there are no clinically significant drug-related adverse tolerability changes on Day 3, subjects will continue dosing BID bilaterally for the remaining dosing period for a total of 8 weeks.
 
The study eye will be designated at randomization. If both eyes have an inferior corneal fluorescein staining score (ICSS) ≥ 2, the study eye will be the one with the greater ICSS. If both eyes have the same ICSS grade, the eye with the higher overall total corneal staining score will be selected. If both eyes show the same total corneal staining score, the eye with the lower tear volume by Schirmer's test will be selected; if both eyes still score equally, the right eye will be selected.
 
Ocular assessments should be conducted by the same assessor throughout a subject's participation period to reduce observer variability. All efficacy assessments will be carried out consistently either in the morning or the afternoon (preferred time window is ± 2 hours) throughout all study visits to minimize intra-subject diurnal variability.
 
During the Baseline visit, all assessments will be carried out before dosing with the study medication in order to serve as pre-study baseline. For on-treatment visits at Weeks 2, 4, and 8, all ocular assessments will take place at least 1 hour after receiving study medication. At Weeks 2, 4, and 8, subjects who arrive in clinic before 1 pm should receive their morning dose administered by clinic staff. Subjects who arrive in clinic after 1 pm should self-administer their morning dose and receive their afternoon/evening dose by clinic staff.
 
A subset of subjects (up to 36) at selected sites will undergo blood collection for pharmacokinetic evaluation of the test article at 3 timepoints (15 and 45 minutes and 3 hours) after final dose of study medication at Week 8.

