Investigational Product, Dose and Mode of Administration:	
Topical, sterile, non-preserved single-use vials of 0.25 mL ocular eye drop:
 
 • ALY688 Ophthalmic Solution 0.1% • ALY688 Ophthalmic Solution 0.4% • Vehicle Ophthalmic Solution (same as ALY688 without active drug)

Study Population:	Subjects with symptomatic DED confirmed by clinical examination
Inclusion Criteria:	
 1. Males or females who are at least 18 years of age at the Screening visit 2. Subject-reported history of dry eye in both eyes for at least 3 months prior to screening 3. Confirmed use, by either medical records or subject self-reporting, of artificial tear substitute for symptoms of DED ≥ 3 times per week on average for the 4 weeks prior to screening (including regular or as needed use of prescription or over-the-counter products) 4. Willing to suspend use of artificial tear substitutes for the duration of study participation 5. Eye dryness score (EDS) using 0- to 100-point visual analog scale (VAS) in both eyes between 40 and 90 (inclusive) at screening and between 30 and 90 (inclusive) at baseline 6. One eye (same eye) must meet all of the following criteria at both screening and baseline: 
 a. Total corneal fluorescein staining score between 6 and 17 (inclusive) using the Expanded National Eye Institute (NEI) scoring system (0-20 scale) b. Inferior corneal fluorescein staining score (ICSS) ≥ 2 (0-4 scale) c. Schirmer's test (without anesthesia) score between 1 and 9 mm/5 min (inclusive) 7. Best-corrected visual acuity (BCVA) of $+0.6$ logarithm of the minimum angle of resolution (logMAR) or better (using Early Treatment Diabetic Retinopathy Study [ETDRS]); Snellen equivalent score of 20/80 or better) and reading Snellen visual acuity of 20/40 (J3) or better in each eye at screening and baseline 8. An understanding, ability, and willingness to fully comply with study procedures and restrictions 9. Ability to voluntarily provide written, signed, and dated (personally or via a legally authorized representative) informed consent to participate in the study 10. For females of childbearing potential, confirmation of a negative urine pregnancy test at screening and baseline and willing to comply with applicable contraceptive requirements detailed in the protocol
Exclusion Criteria:	Ocular history – medical

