	
 1. Confluent (grade 4) fluorescein corneal staining in the superior zone in either eye at screening or baseline 2. Confluent (grade 4) fluorescein corneal staining in 3 or more zones in either eye at screening or baseline 3. Improvement in EDS by more than 25% between screening and baseline (run-in period) 4. Allergic conjunctivitis if active within 4 weeks prior to screening or anticipated to be active during the study 5. Severe meibomian gland dysfunction (MGD) using the Simplified Scheme for Grading MGD (based on central 10 gland orifices of each eyelid) with a score of Grade 3 or greater in the study eye evaluating both the upper and lower eyelids. The subject will be excluded if any of the following are present in either of the evaluated eyelids of the study eye: 
 a. Plugging of meibomian gland: more than 2/3 of glands plugged or >6 glands plugged in either eyelid of the study eye b. Character of secretion: paste or no observable expressate in either eyelid of the study eye c. Expressibility: fewer than 2 glands expressible in either eyelid of the study eye 
NOTE: Mild or moderate (Grade 1 or 2) posterior lid margin disease (MGD) is allowed if the subject has not received topical or systemic treatment (eg, tetracycline, doxycycline, or azithromycin) or mechanical therapy such as lid scrubs, for at least 4 weeks prior to screening and will not receive any such therapy during the study
 
 6. Glaucoma or ocular hypertension requiring treatment within 6 months of screening 7. Use of an intranasal tear stimulant (device or medication) within 4 weeks prior to screening or planned use during the study 8. Unwillingness to avoid wearing contact lenses starting at least 2 weeks prior to screening and during the study 9. DED secondary to scarring (eg, associated with irradiation, alkali burns, Stevens-Johnson syndrome, cicatricial pemphigoid) or destruction of conjunctival goblet cells (as with vitamin A deficiency) 10. Any other clinically significant ocular condition in the study eye that, in the investigator's judgment, is of a severity that adversely affects vision and/or could affect the results of study assessments, including but not limited to: eyelid margin abnormalities (eg, anterior blepharitis, excessive lid laxity, floppy eyelid syndrome, ectropion, entropion), retinal disease (eg, proliferative diabetic retinal disease [minimal early non-proliferative diabetic retinopathy is permitted], age-related macular degeneration [AMD; mild AMD untreated by intravitreal injection is permitted], or retinal vein occlusion), lagophthalmos, exposure keratitis, limbic keratoconjunctivitis, or active ocular or eyelid inflammation, including uveitis 11. Corneal stromal and/or epithelial defects or anatomic abnormalities that, in the investigator's judgment, adversely affect vision and/or could affect the results of study assessment not due to DED (eg, neurotrophic keratitis recurrent corneal erosions, and filaments) 12. Currently active, or history of, ocular herpes or any other ocular infection within 4 weeks prior to screening (with the exception of mild or moderate

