Safety Endpoints:	
To evaluate the safety and tolerability of ALY688 administered BID over 8 weeks compared with Vehicle, as assessed by ocular examinations (including any changes from baseline in slit lamp biomicroscopy, dilated fundus exam, visual acuity, IOP, and post-dosing comfort) and systemic evaluations (AEs, BP and HR, clinical laboratory test results, and pharmacokinetic results [in a subset of subjects]) in subjects with DED.

Efficacy Endpoints:	
To evaluate the efficacy of ALY688 compared with Vehicle by the following measures:
 
 • Mean change from baseline at Weeks 2, 4, and 8 in total corneal fluorescein staining score using the NEI/Industry Workshop scale (0-20 scale). • Mean change from baseline at Weeks 2, 4, and 8 in EDS using a VAS (0-100 scale, both eyes) during the visit. 
NOTE: This will also be assessed by a daily EDS score card for the 7-day period prior to baseline and the Weeks 2, 4, and 8 visits. The mean of these scores for the 7 days prior to the Weeks 2, 4, and 8 visits will be compared with the mean of the scores for the 7 days prior to baseline.
 
Additional exploratory endpoints:
 
 • Mean change from baseline at Weeks 2, 4, and 8 in ICSS (0-4 scale) using the Expanded NEI/Industry Workshop scale (5 zones with 0-4 scale/zone) • Mean change from baseline at Weeks 2, 4, and 8 in ODS using a VAS (0-100 scale, both eyes) 
 ○ NOTE: This will be assessed in the same manner and at the same timepoints as the EDS score • Mean change from baseline at Weeks 2, 4, and 8 in SAnDE score (frequency and severity) based upon subject recollection for the week prior to visit • Mean change from baseline at Weeks 2, 4, and 8 in conjunctival lissamine green staining score using the NEI/Industry Workshop scale (6 zones with 0-4 scale/zone) • Mean change from baseline at Weeks 2, 4, and 8 in conjunctival hyperemia by clinical scoring (0-4 clinical grading scale using standardized grading photos) • Mean change from baseline at Weeks 2, 4, and 8 in TFBUT using fluorescein • Mean change from baseline at Week 2, 4 and 8 in tear volume as assessed by Schirmer's test (without anesthesia) • Mean change from baseline at Week 8 in the following components of the VAS dry eye symptom index: 1) burning/stinging, 2) itching, 3) foreign body sensation, 4) photophobia, and 5) pain. In addition,

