Sample Size and Statistical Methods:	
This is an exploratory, hypothesis-generating study. However, with 40 subjects per group (N=120), there is 80% power to detect an effect size of 0.63 with a 2-sided, two-sample t-test at an alpha level of 0.05 (uncorrected for multiplicity).
 
A repeated measures analysis will be performed using the Wei-Lachin approach. In addition to repeated measures, the Week 8 change from baseline will be tested as a single timepoint measure. An aggregated efficacy measure (specific endpoints TBD) will be analyzed as a means to look for consistent trends and to increase the overall power. For example, an aggregate of ICSS, TFBUT, and Schirmer's test results may be analyzed.
 
The test of the several endpoints involves a comparison of mean change from baseline across visits. A fixed effects longitudinal model will be utilized where the data of both eyes will be used for measures evaluated in both eyes with measures repeated across visits. Baseline score will be a covariate in the model. An unstructured correlation matrix will be utilized for correlation between eyes and across visits. Measures that do not involve both eyes will utilize an unstructured matrix to model the correlation across visits.
 
The randomization will be stratified on study site to achieve a balance among treatment groups within a site. Each site will be preloaded with complete blocks. The site will dispense kits by Interactive Web Response System as subjects qualify for treatment assignment. To the extent possible, study drug resupply to sites will be done with complete block(s).
 
Statistical details will be specified more fully in the Statistical Analysis Plan.

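### The study-eye rule can designate an eye that fails inclusion 6: reconcile the two, and add a supplementary corneal-staining analysis of qualifying eyes beside the unchanged both-eyes model

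*Combined protocol and SAP*

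**What the plan says.** All references are to the Synopsis of the combined protocol and SAP.

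- **Inclusion Criteria, item 6:** "One eye (same eye) must meet all of the following criteria at both screening and baseline". The criteria are total corneal staining 6 to 17 (6a), ICSS of at least 2 (6b) and Schirmer 1 to 9 mm in 5 minutes (6c).
- **Study Design:** if both eyes have ICSS of at least 2, "the study eye will be the one with the greater ICSS". Ties go to higher total staining, then lower Schirmer, then the right eye. Inclusion 6 is not mentioned.
- **Exclusion Criteria, items 5, 10, 15, 16 and 17** apply to the study eye only. Item 5, for example, excludes severe meibomian gland dysfunction "with a score of Grade 3 or greater in the study eye evaluating both the upper and lower eyelids".
- **Exclusion Criteria, items 1 and 2** apply to either eye: "Confluent (grade 4) fluorescein corneal staining in the superior zone in either eye at screening or baseline" and "Confluent (grade 4) fluorescein corneal staining in 3 or more zones in either eye at screening or baseline".
- **Sample Size and Statistical Methods:** "A fixed effects longitudinal model will be utilized where the data of both eyes will be used for measures evaluated in both eyes", with baseline as covariate and unstructured correlation between eyes and visits. The same section provides for measures that do not involve both eyes, and leaves further detail to the SAP.
- **Efficacy Endpoints:** both eyes are specified for the eye dryness and ocular discomfort scores. For corneal staining the number of eyes is not stated. No endpoint, population or model sentence in the supplied text uses the study eye.

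**The concern.** There are two linked points.

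First, eligibility rests on one eye meeting 6a to 6c, while the study eye is picked by a rule that does not look at 6a or 6c. The two can be different eyes. Exclusions meant to keep confounding conditions out of the study eye would then be checked in an eye that does not qualify. A subject whose qualifying eye has, for instance, a prior keratoplasty could be admitted, and one whose qualifying eye is free of such conditions could be turned away.

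Second, subjects are selected on one eye, while the model uses both. If corneal staining is scored in both eyes at Weeks 2, 4 and 8, the estimate averages over fellow eyes that need not meet inclusion 6, and some have little staining to lose. A weak result on total staining, the first efficacy endpoint listed, or on ICSS, part of the example aggregate, could not then be told apart from a floor effect in mild fellow eyes.

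**Working it through.** **1. Study-eye rule against inclusion 6.** Suppose a subject has these values at both screening and baseline:

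| | ICSS | Total | Schirmer | Meets 6a-c? |
|---|---|---|---|---|
| Eye A | 3 | 5 | any | No, fails 6a |
| Eye B | 2 | 8 | 6 mm | Yes |

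Eye A's grades are possible (zones 3, 1, 1, 0, 0) and breach neither exclusion 1 nor 2. The subject is eligible through eye B. Both eyes have ICSS of at least 2, so the rule designates eye A. The same happens through 6c: an eye with ICSS 3 and Schirmer 15 mm is chosen over one with ICSS 2, total 7 and Schirmer 5 mm. The rule states no step for the case where only one eye has ICSS of at least 2, though 6b then leaves only that eye able to qualify.

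**2. How little staining a fellow eye can have.** The scale is described as "Expanded NEI/Industry Workshop scale (5 zones with 0-4 scale/zone"). Exclusion 1 bars grade 4 in the superior zone, and exclusion 2 allows at most two zones at grade 4. With integer grades the highest total is 4 + 4 + 3 + 3 + 3 = 17, which is the upper limit of 6a. A fellow eye failing 6a therefore scores 5 or less at the visit where it fails. One failing 6b at baseline has ICSS 0 or 1 and can improve by at most one grade. The documents give no comparable argument for the other signs.

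**3. The plan's own figure.** With 40 per arm, effect 0.63 SD and two-sided 0.05, the noncentrality is 0.63 × √(40/2) = 2.82. Power is 79.5% by the exact t (78 df) and 80.4% by the normal approximation. The stated 80% reproduces.

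**4. Possible dilution.** Three inputs are absent from the documents and are assumed: q, the share of subjects whose fellow eye does not qualify; f, the response of those eyes as a fraction of that in qualifying eyes; and ρ, the between-eye correlation of change. Assigning 0.63 SD to qualifying eyes, a common SD in all eyes, and a single Week 8 comparison of one dose with Vehicle are also assumptions.

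- All eyes: d = 0.63 × [1 − q(1 − f)/2] / √((1 + ρ)/2)
- Qualifying eyes: d = 0.63 × √[(1 − q) × 2/(1 + ρ) + q]

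For ρ = 0.7 and q = 0.35, the qualifying-eye d is 0.63 × √(0.65 × 2/1.7 + 0.35) = 0.665, with power 83.6%. For all eyes, √(1.7/2) = 0.922:

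| f | Estimate lowered by | All-eyes d | All-eyes power | Change from restricting |
|---|---|---|---|---|
| 0 | 17.5% | 0.63 × 0.825/0.922 = 0.564 | 70.2% | +13 points |
| 0.5 | 9% | 0.63 × 0.9125/0.922 = 0.623 | 78.6% | +5 |
| 0.75 | 4% | 0.63 × 0.956/0.922 = 0.653 | 82.3% | +1 |
| 1 | 0% | 0.63/0.922 = 0.683 | 85.5% | −2 |

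Over ρ 0.3 to 0.8 and q 20% to 75%, restricting changes power by +4 to +36 points at f = 0, +1 to +14 at 0.5, −4 to +5 at 0.75, 0 to −7 at 0.9, and −1 to −9 at 1. The +36 needs f = 0, q = 75% and ρ = 0.8 together. Break-even f is about 0.63, 0.74, 0.85 and 0.90 at ρ = 0.3, 0.5, 0.7 and 0.8.

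**The case against.** Averaging over all treated eyes is a legitimate target. Dosing is bilateral, dry eye history and the dryness score must qualify in both eyes, and the between-eye correlation is modelled. Visual acuity (inclusion 7) and exclusions 11 to 14 and 19 to 21 are not confined to the study eye either, so fellow eyes are far from unselected. Two-eye scoring of staining after baseline is not stated; if only the study eye is scored, the dilution question disappears. The supplied text is a synopsis that defers detail to the SAP and to a Schedule of Events, either of which may settle it. The floor is also modest: an eye with total 5 can still improve by 5 points, against 6 for the mildest qualifying eye, and an eye that fails only on Schirmer has no staining floor. A common SD is doubtful for eyes with ICSS 0 or 1.

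All of this stands, and it rules out a stronger reading that a reader might infer: that the both-eyes model is an error, or that a qualifying-eye model should lead for every sign. The power figures show a trade-off, not a sure gain, and the floor argument covers only total staining and ICSS.

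It can also be said that the study-eye conflict cannot alter a model that uses both eyes. That is true of that model, but the conflict still determines which eye five exclusions are checked in, and so who is enrolled.

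**Conclusion.** The study-eye rule and inclusion 6 are inconsistent as written. This needs no assumption: one pair of eyes shows it. How often it would occur cannot be said from the documents.

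The dilution point is conditional. If corneal staining is scored in both eyes after baseline, and if non-qualifying eyes respond clearly less, the planned estimate understates the effect in qualifying eyes. In the illustration the understatement is 0% to 17.5%, but q, f and ρ are all assumed and the true size is unknown. The documents do not support reading this as bias in the comparison with Vehicle, as inflated type I error, or as a shortfall in the planned power: subjects are randomized, both eyes are dosed, and the 80% reproduces.

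Priority is minor, because the study is exploratory with a safety primary objective. Both changes are cheap, and the second must be made before unmasking to be more than post hoc.

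**What to change.** 1. **Reconcile the study-eye rule with inclusion 6.** State whether the study eye must be an eye that meets 6a to 6c at screening and baseline. Use the ICSS, total staining, Schirmer and right-eye steps only to choose between eyes that are eligible to be the study eye.
2. **Say whether corneal staining is scored in both eyes at Weeks 2, 4 and 8.** If so, keep the both-eyes model as planned and add to the SAP, before unmasking, wording such as: *For total corneal staining and ICSS, a supplementary analysis repeats the planned model using only eyes that met inclusion 6a-c at screening and baseline. Eye status is fixed from data collected before randomization. The number of fellow eyes included is reported for each arm.* Leave all other measures unchanged.

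Every subject who meets inclusion 6 contributes at least one eye, so nobody eligible drops out of the supplementary analysis. The data it needs are the screening and baseline values behind inclusion 6.

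The cost is a clarified eligibility paragraph and one extra analysis. That analysis is less precise if non-qualifying eyes respond equally: under the assumptions above, 1 to 9 points less power than the both-eyes model. It also omits a fellow eye that misses a single limit at a single visit, including one that fails only on Schirmer. The retained both-eyes estimate keeps that information.

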	
the symptom that each subject self-identifies at baseline as the most bothersome will be analyzed separately.
 
 • Mean change from baseline at Week 8 in reading speed as assessed by New International Reading Speed Texts (IReST) in subjects with adequate near visual acuity (BCVA of 20/40 or better) and appropriate language comprehension • Mean change from baseline at Week 8 in conjunctival goblet and lymphocyte cell densities as assessed by impression cytology • Mean change from baseline at Week 8 in selected inflammatory markers in tears from retained Schirmer's tear strips (post hoc analysis) 
 ○ NOTE: Selected measures from those listed above will also be undertaken as part of the Screening visit to determine eligibility; refer to the Schedule of Events for specific evaluations
Analysis Populations:	
Safety and mITT populations: All randomized subjects who receive at least 1 dose of investigational product
 
Per protocol population: All randomized subjects who meet enrollment criteria and complete efficacy evaluations at week 4 or 8

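### No Screening covariate is named for total corneal staining, ICSS or Schirmer's, although each is read twice before randomization: a small missed efficiency, not an error

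*Combined protocol and SAP*

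**What the plan says.** All references are to the Synopsis of the combined protocol and SAP.

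- **Model.** Sample Size and Statistical Methods describes a fixed effects longitudinal model for change from baseline, using both eyes where both are measured. On adjustment it says "Baseline score will be a covariate in the model". No other covariate is named, and further detail is left to the SAP.
- **What baseline is.** Study Design: "During the Baseline visit, all assessments will be carried out before dosing with the study medication in order to serve as pre-study baseline". Baseline is therefore the one set of readings from that visit.
- **Two readings of three signs.** Inclusion 6: "One eye (same eye) must meet all of the following criteria at both screening and baseline". The criteria are total corneal staining (6 to 17 on the 0-20 scale), ICSS (at least 2 on the 0-4 scale) and Schirmer's (1 to 9 mm/5 min).
- **Both eyes for staining.** Exclusion 1 refers to "Confluent (grade 4) fluorescein corneal staining in the superior zone in either eye at screening or baseline", and exclusion 2 likewise to confluent "fluorescein corneal staining in 3 or more zones in either eye at screening or baseline". Corneal zones must therefore be graded in both eyes at both visits.
- **Timing.** After Screening, "qualified subjects will undergo a 14-day run-in period during which they will use Vehicle BID bilaterally". Baseline and randomization follow, so both readings precede assignment.
- **Stated use of the Screening readings.** A note under Efficacy Endpoints says: "Selected measures from those listed above will also be undertaken as part of the Screening visit to determine eligibility". No supplied text gives them a role in the efficacy analysis.

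**The concern.** Total corneal staining is one of the two efficacy measures listed ahead of the additional exploratory endpoints. ICSS and Schirmer's appear in the example of an aggregate measure, whose stated aims include raising power. With 40 subjects per arm, precision is scarce.

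A single clinical reading contains measurement noise, and for the qualifying eye its range is narrowed by the entry limits. Both weaken it as the sole predictor of follow-up. A second reading of the same eye, taken before randomization and already collected, may recover some of that information. If it is left out, variance that could be explained stays in the error term and confidence intervals are somewhat wider than they need be. The comparison across visits could gain most, because averaging Weeks 2, 4 and 8 reduces follow-up noise but not the noise in one Baseline reading.

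**Working it through.** **1. The plan's own figure.** Inputs from Sample Size and Statistical Methods: 40 per group, effect size 0.63, two-sided two-sample t-test, alpha 0.05. The noncentral t with 78 df gives power of 79.5%; the normal approximation gives 80.4%. The exact-t detectable effect at 80% is 0.634. The stated 80% reproduces.

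**2. What a second covariate removes.** Write r_B for the Baseline-to-follow-up correlation, r_S for Screening-to-follow-up and r_SB for Screening-to-Baseline. The proportional fall in residual variance from adding Screening to a model that already has Baseline is the squared partial correlation:

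cut = (r_S − r_B·r_SB)² / [(1 − r_B²)(1 − r_SB²)]

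The documents give none of these correlations; all values below are assumptions.

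- *All equal to ρ.* The formula reduces to [ρ/(1 + ρ)]². For ρ = 0.3 this is 0.09/1.69 = 5.3%; for 0.5, 0.25/2.25 = 11.1%; for 0.8, 0.64/3.24 = 19.8%.
- *Screening 0.1 weaker than Baseline.* With r_B = r_SB = 0.5 and r_S = 0.4: (0.40 − 0.25)²/(0.75 × 0.75) = 0.0225/0.5625 = 4.0%. The pairs 0.6/0.5 and 0.7/0.6 give 4.8% and 4.7%.
- *Geometric decay.* With r_S = r_B·r_SB (for example 0.25 = 0.5 × 0.5) the numerator is zero and so is the gain.

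**3. Total corneal staining with the entry limits applied.** Simulation, one eye per subject, assumed mean 9 and SD 3.5; scores rounded, clipped to 0-20 and selected on 6 to 17 at both Screening and Baseline. Residual variance after regression on Baseline alone was compared with that after regression on Baseline plus Screening.

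| Assumption | Cut at Week 8 | Cut, mean of Weeks 2, 4, 8 |
|---|---|---|
| Stable trait, independent errors, trait share 0.3 to 0.7 | about 3% to 13% | about 7% to 22% |
| Same, half the noise variance shared by Screening and Baseline | about 1.5% to 7% | about 3% to 11% |
| Correlation decaying with time | near 0% to about 6% | near 0% to about 11% |

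In the first row the Screening-Baseline correlation after selection is 0.19 to 0.55. Selection on ICSS and Schirmer's was not modelled, and no estimate was made for those two endpoints.

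**4. Translation to power.** The plan's 0.63 belongs to an unadjusted t-test. To express a cut as power, 0.63 has to be reread as an effect on the residual SD after Baseline adjustment. A cut of c then turns it into 0.63/√(1 − c):

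- c = 1%: power 79.5% → 79.9%
- c = 5%: 0.63/√0.95 = 0.646; power 79.5% → 81.5%
- c = 6%: power → 81.9%
- c = 10%: 0.63/√0.90 = 0.664; power → 83.5%

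Equivalently, the effect detectable at 80% power moves from 0.634 to 0.634 × √0.95 = 0.618 for a 5% cut.

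**The case against.** The case for leaving the plan alone is substantial.

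- **Nothing is wrong as written.** Under randomization, adjustment for one baseline reading is unbiased. The trial is exploratory, its primary objective is safety and tolerability, and many sound plans use one baseline. This stands: the point is an optional refinement.
- **The Synopsis does not say Baseline is the only covariate.** It calls Baseline a covariate and defers detail to the SAP. It does not even say whether site, the stratification factor, enters the model. This stands: one can say only that no Screening covariate is named.
- **Independent reading errors are not documented.** The plan asks for the same assessor throughout, and the same eligibility thresholds apply at both visits, so some error may be common to Screening and Baseline and absent later. This stands, and sharing half the noise roughly halves the gain.
- **The two readings are taken under different conditions.** Screening follows regular artificial tear use; Baseline follows 14 days of Vehicle with tears suspended. Baseline is nearer to follow-up in time and conditions, so decaying correlation deserves at least equal weight. There, the whole Week 8 range lies below a 10% cut.
- **Schirmer's in the fellow eye.** Inclusion 6 guarantees a Screening value only for the qualifying eye. This stands and affects the wording of the fix.

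What the objections do not remove is that the readings for the qualifying eye must exist, that they precede randomization, and that using them cannot bias the comparison.

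**Conclusion.** The point holds as a minor, nearly free gain in precision. For total corneal staining the cut in residual variance could be anywhere from near zero to about 13% at Week 8 and about 22% for the mean across visits. The upper ends require a stable trait and independent reading errors. Shared noise or decaying correlation keeps it to about 7% and 11% or less in the cases tried. The correlations, the mean and the SD are all assumed.

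A reader might infer that the sign endpoints are wrongly analysed, that the trial is underpowered, or that a double-digit variance reduction is there for the taking on all three signs. The documents support none of these. Baseline-only adjustment is valid. The 80% figure rests on an unadjusted t-test, reproduces, and does not depend on this choice. The size of the gain is unknown, and nothing was calculated for ICSS or Schirmer's.

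**What to change.** In the SAP, for the longitudinal models of total corneal staining and ICSS, and of Schirmer's where a Screening value exists for that eye, prespecify the same eye's Screening score as a second covariate beside the Baseline score. Enter it as a separate term, so that any shift over the Vehicle run-in does no harm, and keep change from Baseline as the response. State a rule for a missing fellow-eye Screening Schirmer's value, for example a missing-value indicator. Settle this before unmasking, since a covariate added later would look data-driven.

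The cost is one degree of freedom per model and a few lines of SAP wording. It needs no new visit or procedure.

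### Randomization is stratified by site, but the efficacy analyses in the Synopsis name only baseline score as a covariate; adding a site main effect is a cheap improvement unless the SAP already has it

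*Combined protocol and SAP*

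**What the plan says.** All of this stands in the Synopsis, mostly under Sample Size and Statistical Methods.

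- **Design.** Site is the only stratification factor named: "The randomization will be stratified on study site to achieve a balance among treatment groups within a site". Blocking supports it: "Each site will be preloaded with complete blocks". Block size is not given. Assignment follows qualification: "The site will dispense kits by Interactive Web Response System as subjects qualify for treatment assignment". The last block at a site can therefore remain unfilled.
- **Analysis.** Four efficacy analyses are described. The first is "A repeated measures analysis will be performed using the Wei-Lachin approach". The second is "In addition to repeated measures, the Week 8 change from baseline will be tested as a single timepoint measure". The third is an aggregate measure whose components are still open. The fourth is a fixed effects longitudinal model using both eyes, for which "Baseline score will be a covariate in the model" and "An unstructured correlation matrix will be utilized for correlation between eyes and across visits". None of the four mentions site as a factor, stratum or random effect.
- **Deferral.** "Statistical details will be specified more fully in the Statistical Analysis Plan". That SAP text was not available for this review.
- **Scale.** 120 subjects randomized 1:1:1, 40 per arm (Study Design), at up to 12 sites (Description of Study Sites).

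**The concern.** Balancing arms within site removes between-site differences from the treatment contrast. A model without site does not credit that: the between-site variance stays in the residual, and the reported standard error exceeds the true one. The precision bought by the blocking then goes partly unused.

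The Synopsis does not leave the longitudinal model blank. It gives a covariate, the use of both eyes and the covariance structure, but not the one factor used in randomization. An analyst working from this text alone would probably fit a model without site. If the matter stays open, whether to include site could also become a choice made after results are seen, in a study that already has several analyses, an undefined aggregate and no multiplicity correction.

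**Working it through.** **Inputs from the Synopsis:** 40 per arm, three arms, effect size 0.63, two-sided alpha 0.05, up to 12 sites. **Assumed:** rho, the share of the variance of baseline-adjusted change that lies between sites, taken as 0, 0.02, 0.05 and 0.10. The documents give no value, and none of these is put forward as the realistic one.

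**Step 1: the plan's own figure.** By the normal approximation, power = Φ(0.63 × √(40/2) − 1.96) = Φ(2.817 − 1.960) = Φ(0.857) = 80.4%. The exact two-sample t-test gives 79.5%. The stated 80% reproduces.

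**Step 2: closed form with full balance within site.** With total variance 1, the true variance of a two-arm difference is (1 − rho) × 2/40, while a model without site estimates about 2/40. The standard error is overstated by 1/√(1 − rho), and type I error is 2 × [1 − Φ(1.96/√(1 − rho))].

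| rho | SE ratio | Type I error without site |
|---|---|---|
| 0 | 1.000 | 5.0% |
| 0.02 | 1.010 | 4.8% |
| 0.05 | 1.026 | 4.4% |
| 0.10 | 1.054 | 3.9% |

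Power without site does not fall: Φ(0.857/√0.90) = Φ(0.904) = 81.7% at rho 0.10, against 80.4% at rho 0.

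**Step 3: degrees of freedom at Week 8.** Three arm means and one baseline slope leave 120 − 4 = 116. Twelve sites add 11 indicators, leaving 105.

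**Step 4: simulation of the Week 8 model.** Change was regressed on arm and baseline, with and without site, at effect 0.63, with 40,000 replicates per cell (simulation error of a power difference about 0.1 point). Site sizes were 21, 18, 15, 12, 12, 9, 9, 6, 6, 6, 3, 3 for complete blocks of 3, and 20, 17, 16, 13, 11, 10, 8, 7, 7, 5, 4, 2 for incomplete blocks of 3 or 6. Change in power from adding site, in percentage points:

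| rho | Complete blocks | Incomplete blocks | Incomplete, sites under 6 pooled |
|---|---|---|---|
| 0 | −0.1 | −0.6 to −0.7 | −0.4 |
| 0.02 | +0.4 | −0.3 | 0.0 |
| 0.05 | +1.1 | +0.6 to +0.7 | +0.8 |
| 0.10 | +2.5 | +1.8 to +1.9 | +1.9 to +2.0 |

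With complete blocks, power without and with site is 79.5/79.4%, 79.6/80.0%, 80.1/81.1% and 80.9/83.4%. Type I error without site is 4.8–5.2% at rho 0, falling to 4.0–4.2% at 0.10; with site it is 4.9–5.2%. Shorter repeat runs agree within simulation error. They put the complete-block gain at rho 0.05 as high as 1.3 points, and the loss at rho 0 with incomplete blocks of 6 at about 1 point.

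**Step 5: the other analyses,** 4,000 replicates per cell, so less precise (about 0.4 point for a power difference in the two-eye model). The two-eye, three-visit model assumed correlations of 0.6–0.8 between eyes and 0.5–0.7 between visits, a site offset constant over both, and complete data. Adding site changed power by −0.2 to −0.9 at rho 0, −0.4 to +1.3 at 0.02, +1.3 to +2.3 at 0.05 and +2.5 to +4.0 at 0.10. That test had no small-sample correction, and its type I error was 5.3–6.0% at rho 0 with or without site. A site-stratified Wei-Lachin sum over visits (one eye, no baseline adjustment) changed power by −0.1 to −1.6, −0.7 to +0.4, +0.3 to +1.9 and +1.8 to +3.3 at the same four values. Missing visits, pooling in the longitudinal model and the aggregate measure were not simulated.

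**The case against.** The strongest reply is that this is a synopsis. It defers detail to an SAP not seen here, and naming baseline as a covariate does not exclude others. That stands: a reader might infer that the plan rules site out, and the text does not support that. The request is therefore conditional on what the SAP says.

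Second, no error results. A reader might infer that ignoring the stratification factor invalidates the tests or the power statement. It does neither: without site, type I error falls below nominal when sites differ, the treatment estimate is unbiased, and power does not drop below the stated level. Efficacy is also exploratory here, and the primary objective is safety and tolerability.

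Third, the benefit depends on an unstated rho and changes sign over the range. At 0.02 or less with incomplete blocks, adding site is neutral or slightly costly at Week 8. Features of the plan may keep rho low: the same assessor for each subject, standardized photographs for hyperemia, and baseline adjustment. Grader differences do not reach the subject-reported dryness score. This stands, and no particular gain is claimed as realistic.

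Fourth, pooling is not required. Twelve sites average 120/12 = 10 subjects, about 3.3 per arm, so a site may lack an arm. A main-effect model can still be fitted then, and pooling improved Week 8 power by only about 0.1 to 0.3 point in the incomplete-block layouts. It is a refinement.

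What survives is narrower: the randomization factor is absent from the analyses as described, and naming it costs little.

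**Conclusion.** The point holds as a cheap improvement, not as an error. As described in the Synopsis, the efficacy analyses leave between-site variance in the residual. If sites differ, standard errors are too wide, by 1.6–2.4% at rho 0.05 and 3.7–4.9% at rho 0.10 in the Week 8 simulations, and the tests are mildly conservative. Including site would gain about 0.6 to 1.3 points of Week 8 power at rho 0.05 and about 2 to 2.5 at 0.10. These figures rest on the assumed rho, 12 sites of the sizes shown, and 120 subjects with Week 8 data. Support is firmest for the Week 8 model and weaker for the longitudinal one, whose correlations and constant site offset are also assumptions.

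**What to change.** Unless the SAP already does so, add a short paragraph before unmasking stating that site enters the Week 8 and longitudinal models as a main effect, with no site-by-treatment term.

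Two additions are optional:

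- A rule fixed in advance for combining very small sites. The rule simulated combined sites with fewer than 6 subjects. In the incomplete-block layout this merges the sites of 5, 4 and 2, leaving 10 groups and 116 − 9 = 107 residual degrees of freedom.
- A site-stratified Wei-Lachin test, which needs its own specification and can lose up to 1.6 points of power if sites do not differ.

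The main change costs up to 11 degrees of freedom. If sites do not differ, the Week 8 loss is about 0.1 point of power with complete blocks and up to about 1 point with incomplete blocks; in the two-eye model it is also up to about 1 point. If the SAP already includes site, nothing needs to change.
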